10.3 Interim Analysis

Since this is a pilot study, no interim analysis will be performed. Data analysis will be performed after study enrollment is complete.

10.4 Data Safety Monitoring Plan

The PI will assure that informed consent is obtained prior to performing any research procedures, that all participants meet eligibility criteria, and that the study is conducted according to the IRB-approved research plan. Because this is a pilot study, a formal Data and Safety Monitoring Board will not be formed; instead, a safety officer will oversee and review adverse events during the study period. Please see below regarding the roles of the safety officer.

Frequency of Data and Safety Monitoring

Study data are accessible at all times for PI to review. The PI will review study progress weekly initially (bi-weekly once the study procedures are established), including the number of potential patients screened and provided informed consent, the number of drop-outs, protocol deviations, and adverse events. The PI will review serious adverse events in real-time and consult each other when needed for determination of the relatedness to the study interventions. The PI will ensure that all protocol deviations, adverse events, serious

adverse events, and unanticipated problems are reported to IRB. Serious adverse events and unanticipated problems that are definitively related to the study interventions will be reported to IRB within 48 hours from when we learn about the event.

Content of Data and Safety Monitoring Report

The content of the data and safety monitoring report will include accrual, baseline characteristics, efficacy data on primary and secondary outcomes, and adverse events.

DSMB/Safety Officer

A formal Data Safety Monitoring Board will not be established for this pilot study; however, a physician not directly involved in the study has been identified to fill the safety officer role: [name], a geriatrician and clinical investigator at HSL Marcus Institute and Associate Professor of Medicine, HMS.

Conflict of Interest of DSMB/Safety Officer

The safety officer will have no direct involvement with the study investigators or intervention. The safety officer will sign a conflict-of-interest statement which includes current affiliations, if any, with pharmaceutical and biotechnology companies, and any other relationship that could be perceived as a conflict of interest related to the study and/or associated with commercial interests pertinent to the study objectives.

DSMB/Safety Officer Responsibility

- Assess the research protocol, informed consent documents, and plans for data safety and monitoring
- Recommend initiation of subject recruitment after review of the protocol
- Evaluate trial progress quarterly, including recruitment, accrual and retention, participant risk versus benefit, and other factors that can affect study outcomes
- Consider factors external to the study when relevant, such as scientific or therapeutic developments that may impact the safety of the participants or the ethics of the trial
- Provide recommendations and assist in the resolution of problems reported by the PI
- Protect the safety of the study participants
- Provide recommendations to the PI regarding continuation, termination, or other study modifications based on the observed beneficial or adverse effects of the treatment under study
- Ensure the confidentiality of study data and monitoring results

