8.2 Secondary Outcomes

For *secondary outcomes*, we will measure the following:

- Change in 5-chair stand test (time)
 - Measurement: time to complete 5 chair stands (seconds), post-prehabilitation minus pre-prehabilitation
 - Range: -60 to 60 seconds (higher values indicate worsening performance)
- Change in dominant handgrip strength (kg)
 - Measurement: average of 3 measurements of dominant handgrip strength, post-prehabilitation minus pre-prehabilitation
 - Range: -50 to 50 kg (higher values indicate improved performance)
- Change in protein intake (grams)
 - Measurement: 3-day average protein intake from dietary recall, post-prehabilitation minus pre-prehabilitation
 - Range: -100 to 100 grams (higher values indicate greater intake)
- Adherence to exercise
 - Measurement: proportion of days with ≥ 30 minutes of exercise out of 21-28 days per self-report
 - Range: 0-100% (higher values indicate better adherence)
- Adherence to protein intake
 - Measurement: proportion of oral nutritional supplement consumed over the total number of supplements provided per self-report

- Range: 0-100% (higher values indicate better adherence)
- Adherence to meditation
 - Measurement: proportion of days with ≥ 12 minutes of meditation out of 21-28 days per self-report
 - Range: 0-100% (higher values indicate better adherence)
- Adverse events
 - Measurement: proportion of patients who experience any adverse events per self-report
 - Range: 0-100% (higher values indicate more adverse events)

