10. DATA AND SAFETY MONITORING

10.1 Adverse Events

Definition and Classification of Adverse Events

For this study, the following standard adverse event definitions are used:

- Adverse events: Any unfavorable and unintended sign, symptom, or disease temporally associated with the use of the study intervention, regardless of whether it is considered related to the study intervention.
- Serious adverse event: Any adverse event that result in death, life-threatening experience, hospitalization or prolonged hospitalization, persistent or significant disability or incapacity.
- Unanticipated problems: Any experience that 1) is unexpected in terms of nature, severity, or frequency, given the research procedures described in the protocol document and the characteristics of the study population; 2) is related or possibly related to participation in the research; 3) suggests that the research places participants or others at a greater risk of harm than was previously recognized.

Adverse events are graded according to the following scale:

- Mild: An experience that is transient and requires no special treatment. The experience does not generally interfere with usual daily activities.
- Moderate: An experience that is alleviated with simple therapeutic treatments. The experience impacts usual daily activities.
- Severe: An experience that requires therapeutic intervention. The experience interrupts usual daily activities. If hospitalization (or prolongation of hospitalization) is required for treatment, it becomes a severe adverse event.

The study uses the following adverse event attribution scale:

- Not related: The adverse event is clearly not related to the study procedures (i.e., another cause of the event is most plausible and/or a clinically plausible temporal sequence is inconsistent with the onset of the event).
- Possibly related: An event that follows a reasonable temporal sequence from the initiation of study procedures, but that could readily have been produced by a number of other factors.
- Definitively related: The adverse event is clearly related to the study procedures.

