10.2 Adverse Event Monitoring

Monitoring adverse events will be primarily performed in two ways: 1) unsolicited report from study interventionists (physical therapist, dietitian, and meditation teacher); and 2) weekly assessments by telephone using a standardized checklist.

- Unsolicited reporting: Any adverse events that occur during the in-person or virtual sessions will be assessed for severity by the study interventionists (in conjunction

with PI or an MD co-investigator). In the event of a serious adverse event, the participant or caregiver will be instructed to contact emergency medical services to receive immediate medical attention. All adverse events will be reported to the PI.

- Standardized assessment: At the beginning of cognitive behavioral intervention telephone calls, co-investigator [name] will assess adverse events using a standardized checklist that includes the following expected adverse events (see below).

Expected Adverse Events

- Exercise: fall or injury (expected risk is low); new or worsening musculoskeletal pain (expected risk is moderate); cardiovascular events including angina, arrhythmia, myocardial infarction, heart failure, or stroke (expected risk is very low); other symptoms including chest pain, dizziness/lightheadedness, dyspnea, palpitation, or syncope (expected risk is low).
- Nutrition: gastrointestinal distress such as diarrhea, nausea, constipation (expected risk is moderate); electrolyte imbalance or dehydration (expected risk is low), renal injury from increased renal solute load (expected risk is very low)³⁸ Meditation: psychological distress (expected risk is very low/rare)³⁹
- Outcome measurement: possibility of incidental finding (such as suicidal ideation) through the Patient-Reported Outcomes Measurement Information System (PROMIS) surveys (expected risk is very low)

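### The adverse-event outcome in Section 8.2 counts only self-reported events, and the 48-hour IRB rule in Section 10.4 leaves some unanticipated problems, as Section 10.1 defines them, without a deadline

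*Combined protocol and SAP*

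**What the plan says.** **Adverse-event outcome.** Section 8.2 defines this secondary outcome as the "proportion of patients who experience any adverse events per self-report". Section 10.2 describes two main monitoring routes. One is "unsolicited report from study interventionists (physical therapist, dietitian, and meditation teacher". The other is a weekly telephone assessment with a standard checklist, made at the start of the cognitive behavioral calls. For events arising in sessions, Section 10.2 adds: "All adverse events will be reported to the PI". Table 5 places the outcome before surgery, or in hospital if it was not obtained by then. Neither Table 5 nor Section 11 says which sources feed the proportion.

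**IRB reporting.** Under Section 10.1 an unanticipated problem must be unexpected, must suggest more risk than was previously recognized, and must be one that "is related or possibly related to participation in the research". The adverse-event attribution scale in the same section keeps two positive levels apart: "Possibly related: An event that follows a reasonable temporal sequence from the initiation of study procedures", and "Definitively related: The adverse event is clearly related to the study procedures". Section 10.4 sets a general duty with no time limit, which also takes in protocol deviations: "adverse events, and unanticipated problems are reported to IRB". It then gives the only deadline: "Serious adverse events and unanticipated problems that are definitively related to the study interventions will be reported to IRB within 48 hours".

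**The concern.** In each case a rule is narrower than the section it relies on, and the plan does not say that this is intended.

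For the outcome, the trial collects events by two routes but defines its reported safety proportion by one. An event that a physical therapist saw and recorded could be missing from the figure the pilot publishes and carries into planning of the larger RCT.

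For the deadline, staff who follow Section 10.4 literally have no time limit for some problems that meet the plan's own definition. They could also disagree about whether a possibly related serious adverse event is due within 48 hours. The attribution scale has no level between *possibly* and *definitively* related, so any related event that is not clearly caused by study procedures falls into the lower level.

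**Working it through.** There is no planned figure to reproduce. The check compares the sections and follows the logic.

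**Part 1: the outcome in Section 8.2**

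1. Let S be the set of patients with at least one self-reported event, I the set with at least one interventionist-recorded event, and N the number of patients.
2. Section 8.2 as written gives |S| / N. Counting both Section 10.2 routes gives |S or I| / N.
3. The difference is |I and not S| / N, which is zero or positive. Self-report alone can match the two-source proportion or fall below it, but never exceed it.
4. At the target enrollment of N = 30 (Section 5), each patient in that group moves the proportion by 1/30 = 3.3 percentage points. The documents do not say how many such patients to expect, so this is only the step size, not an estimate of the undercount.
5. The group should be small. Section 2 says the weekly call asks about any potential adverse event, and a patient is lost only if an interventionist records an event while the patient reports none of any kind. It need not be empty, because the checklist depends on the cognitive behavioral calls taking place, and Table 3 treats delivery of those calls as something still to be measured.

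**Part 2: the deadline in Section 10.4**

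1. *Relatedness.* Section 10.1 admits related or possibly related problems. Section 10.4 attaches the deadline to definitively related ones. The scale separates the two levels, so they cannot be read as synonyms.
2. *Related to what.* The definition refers to participation in the research, the attribution scale to study procedures, and the deadline to study interventions. Section 10.2 lists outcome measurement as its own source of adverse events, and Section 12.1 lists loss of confidentiality as a risk. A problem from either source, if it is not also a serious adverse event, could fall outside the deadline even when its link to participation is clear.
3. *Serious adverse events.* If the relatedness clause attaches only to unanticipated problems, every serious adverse event is due in 48 hours. If it attaches to both nouns, a possibly related serious event has no deadline. Grammatically, the word serious could also govern both nouns, which would narrow the rule further.
4. *What is common to all readings.* A non-serious, possibly related unanticipated problem has no stated deadline under any of them.

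**The case against.** The strongest reply on reporting is that an expedited tier may properly be narrower than the definition of what is reportable. The general duty in Section 10.4 still sends every unanticipated problem to the IRB. The PI reviews serious events as they arise and reviews adverse events at regular study-progress checks, and a safety officer oversees the study. These reviews stand and limit the consequence, but none of them sets an IRB deadline for the group left out, and they do not settle how the rule applies to serious adverse events.

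On the outcome, the reply is that a secondary outcome may validly be narrower than safety monitoring. The monitoring report in Section 10.4 lists adverse events separately from the primary and secondary outcomes, so the Section 8.2 wording does not take interventionist reports out of safety review. That also stands. What remains is that the plan neither says the narrower definition is deliberate nor explains it, and the published proportion would follow Section 8.2.

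It is also fair to say that nothing in the documents makes 48 hours the required limit for possibly related problems. They support the need for a stated limit; the choice of limit is open.

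**Conclusion.** Both points hold in limited form. The Section 8.2 proportion can be too low but not too high relative to the events the trial collects. The shortfall is probably small, and its size cannot be derived from the documents. Section 10.4 leaves at least one kind of unanticipated problem without a deadline and leaves its coverage of serious adverse events unclear. The group is narrow, because such a problem must also be unexpected and point to greater risk than was recognized. This rests on reading Sections 8.2 and 10.4 literally, with no unstated local reporting rule filling the gap.

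Three stronger readings are not supported:

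- A reader might infer that possibly related unanticipated problems go unreported. They do not: Section 10.4 requires that they reach the IRB, and only the time limit is missing.
- A reader might infer that interventionist reports are lost to safety oversight. Section 10.2 sends them to the PI.
- A reader might try to express the gap as a share of combinations of seriousness and relatedness. Section 10.1 defines seriousness and the attribution scale for adverse events, whereas an unanticipated problem can be any experience, and the reference term changes between sections. Such counts would not be reliable and would say nothing about expected events.

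Neither point touches the primary outcome, the sample size of 30 or the progression criteria in Section 12.4, none of which uses adverse events.

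**What to change.** **Section 8.2.** Count a patient as having an adverse event if one is recorded from either Section 10.2 source, the weekly telephone assessment or an interventionist report. Report the proportion by source where the source is recorded.

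**Section 10.4.** State a deadline for every unanticipated problem that meets the Section 10.1 definition, and use that definition's reference term, participation in the research. Extending the existing 48 hours is the simplest option, but the sponsor may set another limit if it is stated. In a separate clause, say which serious adverse events the deadline covers.

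**Cost.** One line in Section 8.2 and about two sentences in Section 10.4. The combined count needs no new event collection, since interventionist reports already go to the PI. A breakdown by source does depend on the source being recorded for each event, which the documents do not establish. The downside is a few more expedited IRB reports, whose number cannot be estimated from the documents.

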11. ANALYSIS PLAN

11.1 Statistical Analysis for Feasibility

We will estimate the feasibility of the entire prehabilitation program and each component; mean time for preoperative geriatric assessment; proportion of participants who enroll in the prehabilitation program; proportion of participants who drop out; and rate of missing outcome data. No statistical testing will be performed.

Sample Size Justification: We anticipate that the 3 core components of our prehabilitation program would be completed for 70% of the eligible patients⁹⁻¹⁵ (feasibility of $\geq 50\%$ would be needed for a large RCT). Assuming a 20% margin of error and a lower bound of the 95% confidence interval of 0.50, we will need 30 patients.

11.2 Statistical Analysis for Qualitative Research

There is no statistical analysis for qualitative research.

Sample Size Justification: In most qualitative studies, interviews of 16-24 participants are needed to achieve thematic saturation of data.⁴⁰ Our target enrollment of 30 patients (2 patients per week for 15 weeks), ensures we meet that threshold, and our sample size is sufficient to reach thematic saturation to fully understand the “meaning” of the data.

12. HUMAN SUBJECT PROTECTION AND PROTECTION OF CONFIDENTIALITY

12.1 Risks to Human Subjects

[figure not shown]
The potential risks to study participants include modest risk of physical harm, such as musculoskeletal pain, falls, cardiovascular or pulmonary events from low-intensity exercise; diarrhea, nausea, constipation, electrolyte imbalance, dehydration, or renal injury due to hyperosmolar content of some oral nutrition supplement formulations (Ensure Enlive). There is potential risk for increased anxiety or psychological distress from meditation. Lastly, while none of the PROMIS questions specifically ask about suicide, some of the possible questions through the computer-adaptive test may indicate that the patient is at risk. As such, there is potential risk to uncover suicidal ideation in patients. Loss of confidentiality is another potential risk. We do not anticipate any financial or legal risks.

12.2 Protection Against Risks

To minimize physical harm, the physical therapist will adapt the exercise program according to the participant’s physical capacity, their level of confidence, and the home environment. Prior to participation in exercise, the therapist will encourage participants to express any concerns. Participants will be taught safe exercise techniques. To minimize gastrointestinal (GI) distress, only participants with clinically significant weight loss ($>5\%$

x 1 month; >7.5 x 3 months; 10% x 6 months; 20% x 1 year) or who have a history of taking calorically-dense supplements without issue (confirmed by patient) will be provided the hyperosmolar protein supplemental shake (Ensure). All other participants will be provided with a high protein bar or powder (for patients with swallowing or chewing difficulty, powder can be mixed with a solid puree). Those receiving the shake will be instructed to consume no more than one high calorie, high protein supplement per day and to drink adequate fluids before and after taking supplement. In the event of gastrointestinal distress (nausea, diarrhea or constipation), patient will be instructed to consume supplement in divided doses (no more than 50% in one sitting) or to dilute formula 1:1 with water. If gastrointestinal distress continues, patient will be switched to the protein bar or powder. Due to the lower calorie content, those participants may be instructed to consume an additional high-calorie snack, if needed. . In the event that an incidental finding such as depression or suicidal ideation (SI), a specific protocol is outlined below in **Figure 3** to ensure patient safety:

Figure 3 - Incidental Finding: Depression and suicidal risk

In the case of adverse events, the physical therapist or the participant will be instructed to contact a study physician (for any adverse events) and emergency medical services (for serious adverse events). These procedures will prevent or mitigate the consequences of adverse events.

12.3 Potential Benefits to Human Subjects and Others

The proposed research will provide essential information for the future design of a large clinical trial that examines the impact of a multi-component prehabilitation program on post-operative outcomes in frail older adults undergoing major surgery. Under the current standard of care, frail patients continue to experience complications such as mortality,

readmission, functional decline, and discharge to an institution. The potential benefits to study participants include receiving our study intervention, which targets major risk factors that are modifiable yet rarely addressed in the preoperative period (physical function, nutrition, pain, sleep, anxiety, and cognition), at no cost. These interventions address 4 of the 8 target areas identified by the American College of Surgeons “Strong for Surgery” quality initiative to improve surgical outcomes. Moreover, each component of the intervention was studied to have some level of benefit based on biological plausibility and clinical findings. It is thus reasonably expected that the intervention will provide some benefits to the participants that are more likely to outweigh the modest risk of physical harms from exercise.

12.4 Importance of Knowledge to be gained

We will proceed with a large RCT if all of the progression criteria are met: 1) enrollment (we can enroll ≥ 1.5 patients per week); 2) feasibility (we can deliver an adequate dose of the core interventions to $\geq 50\%$ of participants); 3) adherence ($\geq 50\%$ of participants adhere to the core interventions: ≥ 4 days with 30 minutes of exercise per week, ≥ 4 days with protein intake per week, and ≥ 4 days with 12 minutes of meditation per week); 4) follow-up ($\geq 65\%$ of surviving participants can complete PROMIS assessment on postoperative day 90). If these are not met, we will use information from qualitative interview to revise our study interventions before proceeding to an RCT. We will submit an NIH R01 application in 18 months.

